8.4 Schedule of Visits, Measurements and Dosing

8.4.1 Scheduled Visits

Refer to Appendix 1 for a schedule of visits and measurements.

If a subject is discontinued at a scheduled study visit (i.e. Visit 3), the remaining assessments should be captured on the Unscheduled Visit/ Early Exit Visit pages of the source document and corresponding eCRF. Subjects who screen fail (Screening Visits or Visits 1, 2, or 3) may be scheduled for the Unscheduled Visit at the Investigator's discretion due to follow-up of an ongoing AE.

8.4.2 Unscheduled Visits

For unscheduled visits, the reason for the visit should be clearly documented on the appropriate eCRF, including findings from all evaluations that are completed.

Confidential

Page 32

These visits may be performed in order to ensure subject safety. All information gathered at unscheduled visits should be recorded on the Unscheduled Visit/Early Exit Visit pages of the source document and corresponding eCRF.

Evaluations that may be conducted at an Unscheduled Visit (as appropriate, depending on the reason for the visit), include:

- Assessment of Adverse Events
- Assessment of Concomitant Medications
- Visual Acuity Utilizing an ETDRS chart
- Urine Pregnancy Test (for females of childbearing potential)
- Slit lamp Biomicroscopy

If a randomized subject does not attend their scheduled visit, eCRF pages for missed visits will be skipped. All efforts should be made to schedule the subject for an Exit Visit to complete exit procedures.

8.5 Compliance with Protocol

Subjects who are inappropriately enrolled or no longer fulfill the study eligibility criteria may be discontinued from the study. The reason for such discontinuation will be recorded as “protocol violation” in the source document and on the appropriate page in the eCRF.

Site staff will review concomitant medication by asking subjects if they changed their dosing regimen since their previous visit. The response will be recorded in the source document and on the eCRF at Visits 1, 2, and 3.

All protocol violations, regardless of causation, will be recorded in the subject’s source document as well as eCRF. Major protocol violations will be recorded in the subject’s source document, entered in the eCRF, and reported to the IRB, as per the applicable regulations.

8.6 Subject Disposition

8.6.1 Completed Subjects

A completed subject is one who has not been discontinued from the study.

8.6.2 Discontinued Subjects

Subjects may be discontinued prior to their completion of the study due to:

- subject request/withdrawal
- AEs
- protocol violations

Confidential

Page 33

- administrative reasons (e.g., inability to continue, lost to follow up)
- sponsor termination of study
- other

Note: In addition, any subject may be discontinued for any sound medical reason.

Notification of a subject discontinuation and the reason for discontinuation will be made to Ora and/or sponsor and will be clearly documented on the eCRF. Subjects who are discontinued from the study will not be replaced.

8.7 Study Termination

The study may be stopped at any time by the investigator, the sponsor, and/or Ora with appropriate notification.

8.8 Study Duration

This study consists of four (4) office visits (Screening Visit, Visit 1, Visit 2, and Visit 3) over a period of approximately three to five (3-5) weeks.

8.9 Monitoring and Quality Assurance

During the course of the study, an Ora monitor, or designee, will make routine site visits to review protocol compliance, assess IP accountability, and ensure the study is being conducted according to the pertinent regulatory requirements. The review of the subjects' medical records will be performed in a manner that adequately maintains subject confidentiality. Further details of the study monitoring will be outlined in a monitoring plan.

Regulatory authorities of domestic and foreign agencies, Ora quality assurance and/or its designees may carry out on-site inspections and/or audits which may include source data checks. Therefore, direct access to the original source data will be required for inspections and/or audits. All inspections and audits will be carried out giving consideration to data protection as well as subject confidentiality to the extent that local, state, and federal laws apply.

9 ADVERSE EVENTS

9.1 Adverse Event

An AE is defined as any untoward medical occurrence associated with the use of an IP in humans, whether or not considered IP-related. An AE can be any unfavorable and unintended sign (e.g., an abnormal laboratory finding), symptom, or disease temporally associated with the use of an IP, without any judgment about causality. An AE can arise

Confidential

Page 34

from any use of the IP (e.g., off-label use, use in combination with another drug or medical device) and from any route of administration, formulation, or dose, including an overdose. An AE can arise from any delivery, implantation, or use of a medical device, including medical device failure, subject characteristics that may impact medical device performance (e.g., anatomical limitations), and therapeutic parameters (e.g., energy applied, sizing, dose release, and anatomic fit) associated with medical device use.

All AEs spontaneously reported by the subject and/or in response to an open question from study personnel or revealed by observation, physical examination or other diagnostic procedures will be recorded in the source document and on the appropriate pages of the eCRF. Any clinically relevant deterioration in clinical finding is considered an AE and must be recorded. When possible, signs and symptoms indicating a common underlying pathology should be noted as one comprehensive event.

Documentation regarding the AE should be made as to the nature, date of onset, end date, severity, and relationship to IP, action(s) taken, seriousness, and outcome of any sign or symptom observed by the physician or reported by the subject upon indirect questioning.

Ocular complaints should not be addressed as AEs unless the complaint is outside the normal limits for allergic conjunctivitis symptoms after allergen exposure or is associated with clinical sequelae (i.e., adverse slit lamp examination finding).

9.1.1 Severity

Severity of an AE is defined as a qualitative assessment of the degree of intensity of an AE as determined by the investigator or reported to him/her by the subject. The assessment of severity is made irrespective of relationship to IP or seriousness of the event and should be evaluated according to the following scale:

- **Mild:** Event is noticeable to the subject, but is easily tolerated and does not interfere with the subject's daily activities.
- **Moderate:** Event is bothersome, possibly requiring additional therapy, and may interfere with the subject's daily activities.
- **Severe:** Event is intolerable, necessitates additional therapy or alteration of therapy, and interferes with the subject's daily activities.

9.1.2 Relationship to Investigational Product

The relationship of each AE to the IP should be determined by the investigator using these explanations:

- **Suspected:** A reasonable possibility exists that the IP caused the AE. A suspected AE can be further defined as:
 - **Definite:** Relationship exists when the AE follows a reasonable sequence from the time of IP administration, follows a known response pattern of the drug

Confidential

Page 35

class, is confirmed by improvement on stopping the IP and no other reasonable cause exists.

- *Probable*: Relationship exists when the AE follows a reasonable sequence from the time of IP administration, follows a known response pattern of the drug class, is confirmed by improvement on stopping the IP and the suspect IP is the most likely of all causes.
- *Possible*: Relationship exists when the AE follows a reasonable sequence from the time of IP administration, but could also have been produced by the subject's clinical state or by other drugs administered to the subject.
- ***Not Suspected***: A reasonable possibility does not exist that the IP caused the AE.
 - *Not Related*: Concurrent illness, concurrent medication, or other known cause is clearly responsible for the AE, the administration of the IP and the occurrence of the AE are not reasonably related in time, OR exposure to IP has not occurred.

Suspected adverse reaction means any AE for which there is a reasonable possibility that the IP caused the AE. "Reasonable possibility" means there is evidence to suggest a causal relationship between the IP and the AE. Types of evidence that would suggest a causal relationship between the IP and the AE event include: a single occurrence of an event that is uncommon and known to be strongly associated with IP exposure (e.g., angioedema, hepatic injury, Stevens-Johnson Syndrome); one or more occurrences of an event that is not commonly associated with IP exposure, but is otherwise uncommon in the population exposed to the IP (e.g., tendon rupture); an aggregate analysis of specific events observed in a clinical trial (such as known consequences of the underlying disease or condition under investigation or other events that commonly occur in the study population independent of drug therapy) that indicates those events occur more frequently in the IP-treatment group than in a concurrent or historical control group.

9.1.3 Expectedness

The expectedness of an AE should be determined based upon existing safety information about the IP using these explanations:

- ***Unexpected***: An AE that is not listed in the Investigator's Brochure (IB) or is not listed at the specificity or severity that has been observed.
- ***Expected***: An AE that is listed in the IB at the specificity and severity that has been observed.
- ***Not applicable***: An AE unrelated to the IP.

Adverse events that are mentioned in the IB as occurring with a class of products or as anticipated from the pharmacological/mechanical (or other) properties of the product, but are not specifically mentioned as occurring with the particular product under investigation are to be considered unexpected.

Confidential

Page 36

The investigator should initially classify the expectedness of an AE, but the final classification is subject to the Medical Monitor's determination.

9.2 Serious Adverse Events

An AE is considered serious if, in the view of either the investigator or sponsor, it results in any of the following outcomes:

- Death;
- A life-threatening AE;

Note: An AE is considered "life-threatening" if, in the view of either the investigator or sponsor, its occurrence places the subject at immediate risk of death. It does not include an AE that, had it occurred in a more severe form, might have caused death.

- Inpatient hospitalization or prolongation of existing hospitalization;

Note: The term "inpatient hospitalization" refers to any inpatient admission (even if less than 24 hours). For chronic or long-term inpatients, inpatient admission includes transfer within the hospital to an acute/intensive care inpatient unit. Inpatient hospitalization does not include: emergency room visits; outpatient/same-day/ambulatory procedures; observation/short stay units; rehabilitation facilities; hospice facilities; nursing homes; or clinical research/phase 1 units.

Note: The term "prolongation of existing hospitalization" refers to any extension of an inpatient hospitalization beyond the stay anticipated or required for the reason for the initial admission as determined by the investigator or treating physician.

- A persistent or significant incapacity or substantial disruption of the ability to conduct normal life functions;

Note: A serious adverse event (SAE) specifically related to visual threat would be interpreted as any potential impairment or damage to the subject's eyes (e.g., hemorrhage, retinal detachment, central corneal ulcer or damage to the optic nerve).

- A congenital anomaly/birth defect.

Important medical events that may not result in death, are life-threatening, or require hospitalization may be considered serious when, based upon appropriate medical judgment, they may jeopardize the subject and may require medical or surgical intervention to prevent one of the outcomes listed in this definition.

9.3 Procedures for Reporting Adverse Events

All AEs and their outcomes must be reported to Ora, the sponsor, and the IRB/IEC as required by the IRB/IEC, federal, state, or local regulations and governing health authorities and recorded on the appropriate eCRF.

Confidential

Page 37

Collection of AEs/SAEs will begin at the time of informed consent.

9.3.1 Reporting a Suspected Unexpected Adverse Reaction

[figure not shown]
All AEs that are ‘suspected’ and ‘unexpected’ are to be reported to Ora, the sponsor and the IRB/IEC as required by the IRB/IEC, federal, state, or local regulations and governing health authorities.

9.3.2 Reporting a Serious Adverse Event

To ensure subject safety, all SAEs, regardless of relationship to the IP, must be immediately reported. All information relevant to the SAE must be recorded on the appropriate eCRFs. The investigator is obligated to pursue and obtain information requested by Ora and/or the sponsor in addition to that information reported on the eCRF. All subjects experiencing a SAE must be followed up and the outcome reported.

In the event of a SAE, the investigator must notify Ora and the sponsor immediately; obtain and maintain in his/her files all pertinent medical records, information, and medical judgments from colleagues who assisted in the treatment and follow-up of the subject; provide Ora and the sponsor with a complete case history, which includes a statement as to whether the event was or was not suspected to be related to the use of the IP; and inform the IRB of the SAE within their guidelines for reporting SAEs. All SAEs, regardless of expectedness or relationship to the IP, will be reported to the FDA as soon as possible but no later than 15 calendar days after becoming aware of the event.

Contact information for reporting SAEs:

9.4 Procedures for Unmasking (if applicable)

When medically necessary, the investigator may need to determine what treatment has been assigned to a subject. When possible (i.e., in non-emergent situations), Ora and/or the sponsor should be notified before unmasking IP.

Confidential

Page 38

9.5 Type and Duration of the Follow-up of Subjects after Adverse Events

AEs will be followed until:

- Resolution (return to baseline status or to “normal”)
- Stabilization of the event has occurred (no improvement or worsening expected by the investigator)
- Event is otherwise explained, regardless of whether the subject is still participating in the study
- Principal investigator determines, for events that do not end (i.e., metastasis), the condition to be chronic. The event can be determined to be resolved or resolved with sequelae.

The Investigator will follow unresolved adverse events to resolution until the subject is lost to follow-up or until the adverse event is otherwise explained. If the subject is lost to follow-up, the Investigator should make three (3) reasonable attempts to contact the subject via telephone, post, or certified mail. All follow-up will be documented in the subject's source document. Non-serious adverse events identified on the last scheduled contact must be recorded on the AE eCRF with the status noted and be followed as aforementioned.

If the Investigator becomes aware of any new information regarding a Serious Adverse Event (i.e., resolution, change in condition, or new treatment), a new Serious Adverse Event/Unanticipated Report Form must be completed and faxed to Ora Inc. within 24 hours. The original SAE form is not to be altered. The report should describe whether the event has resolved or continues and how the event was treated.

10 STATISTICAL HYPOTHESES AND METHODS OF ANALYSES

10.1 Study Populations

10.1.1 Intent-to-Treat Population

[REDACTED]

10.1.2 Per-Protocol Population

[REDACTED]

Confidential

Page 39

deviations. This population will be analyzed as treated using observed data only for confirmatory analyses. Major protocol deviations will be determined prior to unmasking any subject data.

10.1.3 Safety Population

The safety population includes all subjects who received the test article. The safety population will be analyzed as treated and will be used for the safety analyses. No data will be excluded for any reason.

10.2 General Imputation Methods

Missing data is not expected in this single, post-randomization visit study.

10.3 Statistical Hypotheses

The statistical hypotheses for the non-inferiority test between EM-100 ophthalmic solution and Zaditor® are as follows:

PRIMARY:

SECONDARY:

Conditional upon H_{01} being rejected, the statistical hypothesis for the superiority test between EM-100 ophthalmic solution and vehicle solution will be tested as follows:

H_{02} :

Confidential

Page 40

[REDACTED]

Conditional upon H_{01} and H_{02} being rejected, the statistical hypothesis for the superiority test between Zaditor® and vehicle solution will be tested as follows:

[REDACTED]

[REDACTED]

Conditional upon H_{01} , H_{02} , and H_{03} being rejected, the statistical hypothesis for the non-inferiority test between EM-100 ophthalmic solution and Zaditor® will be tested as follows:

[REDACTED]

[REDACTED]

10.4 Sample Size

The following treatment combinations will be randomized. The eye receiving each test article will also be randomized:

- [REDACTED] with EM-100 in right eye and Zaditor® in left eye
- [REDACTED] with Zaditor® in right eye and EM-100 in left eye
- [REDACTED] with EM-100 in right eye and Vehicle in left eye
- [REDACTED] with Vehicle in right eye and EM-100 in left eye
- [REDACTED] with Zaditor® in right eye and Vehicle in left eye
- [REDACTED] with Vehicle in right eye and Zaditor® in left eye

This sample size requires a total of 60 randomized subjects, while providing [REDACTED]

[REDACTED]

Confidential

Page 41

This sample size will provide [REDACTED]

[REDACTED]

[REDACTED]

[REDACTED]

[REDACTED]

[REDACTED]

10.5 Primary Efficacy Analyses

The primary efficacy endpoint is ocular itching assessed at 3(± 1), 5(± 1), and 7(± 1) minutes post-CAC [REDACTED]

[REDACTED]

[REDACTED]

[REDACTED]

[REDACTED]

Confidential

Page 42

Page 10 of 10

Amendment 2.0/04Apr2018

EyeMax, LLC

Amendment 2.0/04Apr2018

10.6 Secondary Efficacy Analyses

Analyses will be performed on the secondary endpoint of conjunctival redness in a manner similar to the non-inferiority test of the primary endpoint. [REDACTED]

10.7 Adjustment for Multiplicity

Confidential

Page 43

[REDACTED]

10.8 Demographic and Baseline Medical History

The demographic and baseline medical history data will be summarized descriptively overall subjects and for each treatment combination. For quantitative variables, the summaries will include the number of observations, mean, standard deviation, median, minimum, and maximum. Qualitative variables will be summarized using counts and percentages.

10.9 Safety Analysis

Safety will be assessed by evaluating the incidence of subjects with any adverse events during the entire study. The percentage of subjects with any AEs will be summarized, as well as the percentage of subjects with any treatment-emergent adverse events (TEAEs), summarized for each treatment combination. Ocular TEAEs will similarly be summarized by eye for each treatment group. Incidence will be tabulated by MedDRA System Organ Class and preferred term within each system organ class. Adverse events will also be summarized for treatment-related TEAEs, SAEs, by maximal severity, and by day of onset relative to the start of treatment.

The additional safety variables of slit lamp biomicroscopy and visual acuity will be summarized descriptively using quantitative and qualitative summary statistics as appropriate. In all cases, outcomes will be summarized by eye for each treatment group. Changes and shifts from baseline will also be summarized where applicable.

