8.3.1.4 VISIT 3 (Day 1): Enrollment/Randomization/ In-Office Instillation/ Efficacy CAC/ Study Exit

- Update of Medical/Medication History
- Adverse Event Query
- Urine Pregnancy Test (for females of childbearing potential)
- Visual Acuity Utilizing an ETDRS Chart: A clinically significant visual acuity decrease from Visit 1 may be documented as an AE per the investigator's discretion. An increase of [REDACTED] or more should be brought to the attention of the investigator. Visual Acuity may be repeated in instances of significant decreases.
- Pre-CAC Ocular and Nasal Allergic Signs and Symptoms Assessments: The investigator and the subject will assess pre-CAC ocular and nasal allergic signs and symptoms using the Ora-CAC® scales. Subjects exhibiting a sign and/or symptom of allergic conjunctivitis [REDACTED] [REDACTED] will be excluded.
- Slit Lamp Biomicroscopy
- Review of Inclusion/Exclusion Criteria
- Randomization: Subjects who meet all of the inclusion criteria and none of the exclusion criteria and qualify to continue in the study will be enrolled and randomized to receive EM-100, Zaditor®, or the vehicle of EM-100. A separate treatment will be assigned to each eye. Subjects will be assigned the lowest four (4) digit randomization number available.
- Investigational Product Instillation: A trained study technician will instill one drop of the assigned treatment in the right eye and one drop of the assigned treatment in the left eye, according to the directions for use. The investigational product kit number and the time of instillation will be recorded. The pre-specified technicians responsible for instilling the investigational product will not be involved with any other study procedures at the site.
- Efficacy CAC: Each subject will receive one drop of the allergen solution of the same, final dose that elicited a positive reaction at Visit 1 bilaterally, 15(+1) minutes post-instillation of investigational product.
- Post-CAC Ocular and Nasal Allergic Signs and Symptoms Assessments: Assessments of itching will be made by the subject at 3(±1), 5(±1), and 7 (±1) minutes following allergen challenge. Assessments of redness and chemosis will be graded by the

Confidential

Page 31

Investigator at 7(± 1), 15(± 1), and 20(± 1) minutes post-challenge and assessments of eyelid swelling, tearing/watery eyes, ocular mucous discharge, and nasal symptoms will be made by the subject at 7(± 1), 15(± 1), and 20(± 1) minutes post-challenge (Appendix 2).

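### Does recording adverse event onset only to the day weaken the safety analysis at Visit 3, where drop and allergen challenge are 15 to 16 minutes apart?

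*Combined protocol and SAP*

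**What the plan says.** All references are to Amendment 2.0.

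- **Recording.** Section 9.1: "Documentation regarding the AE should be made as to the nature, date of onset, end date, severity". No clock time of onset is named.
- **Tabulation.** Section 10.9 summarizes events "by maximal severity, and by day of onset relative to the start of treatment". It adds: "Ocular TEAEs will similarly be summarized by eye for each treatment group".
- **Visit 3 sequence.** Section 8.3.1.4: "The investigational product kit number and the time of instillation will be recorded". The challenge uses the "same, final dose that elicited a positive reaction at Visit 1 bilaterally, 15(+1) minutes post-instillation of investigational product". The post-challenge assessments, exit examinations, optional relief drop, closing adverse event query and study exit follow on the same day. The only other listed query at that visit comes before the drop.
- **Rules that refer to sequence.** Section 9.1.2 opens the Definite, Probable and Possible grades with "Relationship exists when the AE follows a reasonable sequence from the time of IP administration". Section 9.1 adds: "Ocular complaints should not be addressed as AEs unless the complaint is outside the normal limits for allergic conjunctivitis symptoms after allergen exposure".

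**The concern.** The synopsis lists ocular burning, stinging and irritation as risks of ketotifen drops. The challenge is meant to provoke ocular symptoms within minutes. If onset is known only to the day, an event that began on the drop alone and one that began after the allergen share one date and one table row. The time of instillation is recorded, but the plan names no onset time to set against it.

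Three things seem to be at stake: the relationship rating, which refers to sequence from dosing; the summary of treatment-related events, which rests on that rating; and the rule that ordinary allergic complaints after exposure are not adverse events. A clock time or a three-level flag (before dose, dose to challenge, after challenge) looks like a cheap remedy.

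**Working it through.** No power or error rate is involved. The check is the timing arithmetic, then a look at what in the plan depends on the order of drop and challenge.

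**1. Timing (section 8.3.1.4)**

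- Drop to challenge: 15(+1) gives 15 to 16 minutes.
- Challenge to last redness grade: 20(±1) gives 19 to 21 minutes.
- Drop to last grade: 15 + 19 = 34 to 16 + 21 = 37 minutes.
- Age at the last grade of an event that began between drop and challenge: 19 minutes (onset just before a challenge graded at 19) to 16 + 21 = 37 minutes (onset at the drop).
- Share of a one-day unit taken by the drop-only interval: 15/1440 = 1.04% to 16/1440 = 1.11%.

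A by-day table gives one post-dose category for Visit 3; a flag would give two. The premise holds: the stated timing does not order a post-dose event against the challenge.

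**2. Relationship rating (section 9.1.2)**

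- *Definite* and *Probable* also require that the event eases once the product is stopped. With one drop there is nothing to stop, so an onset time does little to make these grades reachable.
- *Possible* needs a plausible sequence from dosing and allows that the event might also be due to the subject's "clinical state or by other drugs administered to the subject". An event arising during the visit meets this on either side of the challenge, since the last grade is at most 37 minutes after the drop.
- *Not Related* is where order can matter: an event that began before the challenge cannot be blamed on the allergen. The investigator makes that judgement from spontaneous reports, observation and questioning, not from a table of onset dates.

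**3. The allergic-complaint rule (section 9.1)**

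A complaint judged to be an ordinary allergic symptom is not entered as an adverse event. If a sting from the drop were misjudged in this way, it would never reach the form that holds the onset field. A finer field on recorded events cannot reveal it.

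**4. Counts and comparison (section 10.9)**

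An ocular event with onset after dosing enters the by-eye table whatever caused it. Moving the cause from drop to challenge changes the count by 0. Both eyes of each subject receive the same challenge, and treatments are randomized to eyes with vehicle as a control. An excess on one treatment over another is therefore not explained by the allergen.

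**5. What the by-day summary is for**

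Collection starts at consent (section 9.3), and three visits precede dosing. Day of onset separates those earlier events from Day 1, and the opening query at Visit 3 picks up events present before the drop.

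**6. What a flag would deliver**

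Taken at the existing exit query, it relies on recall for events not reported when they began. If the exit procedures take 10 to 20 minutes (an assumption; no durations are given), recall for an event that began between drop and challenge is 19 + 10 = 29 to 37 + 20 = 57 minutes. With 60 subjects, each treatment's events would be split into two small cells. An event that began after the challenge could still be due to the drop.

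**The case for a change.** The strongest reply is that comparing eyes cannot answer every question. Every randomized subject has a drop in both eyes, so there is no undosed eye. Irritation common to all three solutions cannot be told from the allergen reaction by comparing treatments. Non-ocular events cannot be assigned to an eye at all. Every treatment combination includes at least one ketotifen drop, and rhinorrhea is both a listed drug risk and a symptom scored after the challenge. For such events the order of onset is the most direct evidence available, and one extra field is cheap.

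This stands as far as it goes. Onset order would help describe those events and could inform a Not Related rating. But the plan makes no claim about irritation common to all solutions, and its objectives are comparisons of itching and redness between treatments. The gain is limited to describing single recorded events, of unknown and probably small number.

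The gap itself is also unconfirmed. Section 9.1 lists what to document and does not rule out a time. Section 11.6 asks for contemporaneous source data. The case report form is not among the documents, and the Appendix 1 schedule is not shown in the copy reviewed.

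**Conclusion.** The observation is accurate and the consequence is small. Followed as written, the plan gives the same by-eye counts of ocular treatment-emergent events (change of 0), the same randomized comparison and the same primary itching analysis. The Possible rating is available on either side of the challenge, and a finer onset field could not audit the allergic-complaint rule. What is left is finer description of some Visit 3 events, whose number cannot be computed because no event rates are given.

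This rests on two assumptions: that treatment-emergent means onset after dosing (the definition is not visible), and that investigators rate relationship from the full account of the event. If the case report form has no onset time, adding one is a sensible option, but no conclusion of the trial depends on it.
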